### 10.2. Treatment Compliance

Compliance with treatment dosing is to be monitored and recorded by site staff.

Subjects enrolled should be instructed by site staff to return used and unused pens to the site for accountability.

### 10.3. Continuation of Treatment

No further provisions are made for access to the study treatment.

#### **10.4. Concomitant Therapy**

The investigator and/or study personnel will record all concomitant medications taken by the subject during the study from the date of signature of informed consent. Any medications considered necessary for the subject's welfare, and which will not interfere with the study medication, may be given at the discretion of the investigator. Administration of all concomitant medications must be reported in the appropriate section of the CRF along with dosage information, dates of administration and reasons for use. The following conditions should be addressed by the investigator with particular attention, documenting specifically the reasons for the administration of a concomitant medication for the following cases:

- For a MS related condition (e.g. pain, fatigue or weakness and relapses).
- Recording Concomitant Medication from 30 days before baseline.

No interaction studies have been performed. The clinical studies indicate that multiple sclerosis patients can receive Plegridy and corticosteroids during relapses. Interferons have been reported to reduce the activity of hepatic cytochrome P450-dependent enzymes in humans and animals. Caution should be exercised when Plegridy is administered in combination with medicinal products that have a narrow therapeutic index and are largely dependent on the hepatic cytochrome P450 system for clearance, e.g. antiepileptics and some classes of antidepressants.

## **11. STUDY TREATMENT MANAGEMENT**

Study treatment must be stored in a secure location. Accountability for study treatment is responsibility of the Investigator. More details concerning this responsibility are included in Section 11.2.

Study treatment must only be dispensed by a Pharmacist or appropriately trained staff.

Study treatment is to be dispensed only to subjects enrolled in this study.

The study treatment is supposed to be self-administered by the enrolled subjects. Study site staff should train enrolled subjects in the proper technique for self-administering subcutaneous injections using the prefilled pen.

Subjects should be advised to rotate sites for subcutaneous injections. The usual sites for subcutaneous injections are abdomen, back of the upper arm, and thigh.

Study site staff and enrolled subjects should refer to the approved package insert for specific instructions on the handling, preparation, administration, and disposal of the study treatment.

### **11.1. Peg –IFN (PLEGRIDY®)**

Plegridy® is supplied in a single-use, disposable, pre-filled pen that uses a spring-driven mechanism. The following doses of 20 kDa mPEG-O-2-methylpropionaldehyde-modified human IFN  $\beta$ -1a in 20 mM acetic acid/sodium acetate buffer pH 4.8, 150 mM arginine hydrochloride, and 0.005% Polysorbate 20 are provided:

- 63 micrograms of peginterferon beta-1a in 0.5 mL solution for the first injection.
- 94 micrograms of peginterferon beta-1a in 0.5 mL solution for the second injection
- 125 micrograms of peginterferon beta-1a in 0.5 mL solution for the subsequent injections.

The label will include conditions for storage, lot number, and other pertinent information.

#### **11.1.1. Plegridy® Preparation**

The individual preparing Plegridy® should first carefully review the instructions provided in the approved package insert.

If the packaging is damaged, or if there is anything unusual about the appearance or attributes of the prefilled pen or drug, it should not be used. The pen in question should be saved at the study site and the problem immediately reported to Biogen Italia.

Plegridy® is to be stored at 2°C to 8°C, in a monitored, locked refrigerator with limited access.

Plegridy® must not be frozen; it has to be stored in the refrigerator at 2°C-8°C and stored in the original package in order to be protected from light. Plegridy® can be stored at room temperature (2°C to 25°C) for up to 30 days as long as it is stored away from light. If Plegridy® is at room temperature for more than 30 days, it should not be used and must be returned to the Investigator.

The Investigator must return all unused pre-filled pens of Plegridy® as instructed by Biogen Italia

If any Plegridy supplies are to be destroyed at the site, the institution/Principal Investigator(s) must obtain prior approval by Biogen Italia. After such destruction, the institution/Principal Investigator(s)

must notify Biogen Italia, in writing, of the method of destruction, the date of destruction, and the location of destruction.

### **11.2. Plegridy® Accountability**

The study site must maintain accurate records demonstrating dates and amount of study treatment received, to whom dispensed (subject-by-subject accounting), amount returned by the subject, and accounts of any study treatment accidentally or deliberately destroyed.

Unless otherwise notified, all pens both used and unused, must be saved for study treatment accountability. At the end of the study, reconciliation must be made between the amount of Plegridy® supplied, dispensed, and subsequently returned to Biogen Italia. A written explanation must be provided for any discrepancies.

## **12. DISCONTINUATION FROM STUDY TREATMENT AND/OR STUDY WITHDRAWAL**

### **12.1 Discontinuation from study treatment**

A subject *must* permanently discontinue from Peg-IFN for any of the following reasons:

- The subject becomes pregnant.
- The subject withdraws consent.
- The subject experiences a medical emergency that necessitates permanent discontinuation of study treatment.
- At the discretion of the Investigator for medical reasons.
- At the discretion of the Investigator or Sponsor for noncompliance.
- Lost to follow up.

The reason for discontinuation from study treatment must be recorded in the subject's CRF.

All efforts must be made by the Investigator to perform the Early Termination Visit (ET visit) to Subjects discontinuing from treatment. However, the ET visit form will have to be filled by the investigator also for patients that are lost to follow up.

Subjects discontinuing from study treatment for any of the abovementioned reasons must be permanently withdrawn from the study.

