## 4.2. Schedule of Events

Tests and assessment	T0 (Enrollment)	T1 (12 weeks) ± 1 week	T2 (24 weeks) ± 1 week	ET Early termination
Inclusion/Exclusion criteria	X			
Informed consent	X			
Social-demographics (e.g., age, gender)	X			
Medical history (e.g., disease duration, previous disease history and treatments)	X			
On-treatment medical information (e.g., concomitant therapies, comorbidities)	X	X	X	X
Pregnancy hCG test	X			
Clinical and neurological evaluation (including recording of relapses and EDSS)	X	X	X	X
Drug Supply	X	X		
Assessment of patients' satisfaction (TSQM-9)	X	X	X	X
Assessment of patients' adherence	X	X	X	X
Assessment of patients' injection-system satisfaction (Adapted MSTCQ)	X	X	X	X
Assessment of patients' HRQoL (MusiqoL)	X	X	X	X
Assessment of patients' fatigue (FSS)	X	X	X	X
Routine Laboratory tests	X	X	X	X
Adverse events, pregnancy exposure, episodes of overdose		X	X	X
Drug Accountability 		X	X	X

1. If a dose is missed, it should be administered as soon as possible, within 7 days.

CONFIDENTIAL

The information contained herein may not be used, disclosed, or published without the written consent of Biogen Italia

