### **12.2 Withdrawal of Subjects From Study**

Subjects must be withdrawn from the study for any one of the following reasons:

- The subject withdraws consent.
- The subject is unwilling or unable to comply with the protocol.
- The subject meets any of the criteria defined in Section 12.1
- The reason for the subject's withdrawal from the study must be recorded in the subject's CRF.

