The secondary objectives of this study are to evaluate in this study population:

- effects of Peg-IFN beta-1a treatment on patients' satisfaction at 24 weeks;
- effects of Peg-IFN beta-1a treatment on short-term patients' adherence;
- effects of Peg-IFN beta-1a treatment on patients' fatigue;
- effects of Peg-IFN beta-1a on disease activity and physical disability;
- impact of Peg-IFN beta-1a treatment on patient-reported health-related quality of life;
- impact of Peg-IFN beta-1a treatment on patients' injection-system satisfaction;
- evaluate the relationship between patients' satisfaction and adherence;
- evaluate the relationship between patients' satisfaction and social-demographic factors (age, sex, employment working, level of education, etc) and clinical characteristics (ARR, disability, etc.)
- evaluate the treatment safety and tolerability.

4. Inclusion/exclusion criteria

Inclusion Criteria

- ✓ Ability to understand the purpose and risks of the study and provide signed and dated informed consent and authorization to use protected health information (PHI) in accordance with national and local subject privacy regulations.
- ✓ Aged between 18 and 65 years old inclusive, at the time of informed consent.
- ✓ Subjects diagnosed with Relapsing Remitting MS according to 2010 McDonald criteria.
- ✓ Subjects with EDSS score between 0.0 and 5.0 at baseline.

- ✓ Treatment with injectable subcutaneous Interferons with score < 58 in the “convenience satisfaction” domain of TSQM-9.
- ✓ Period of stability from last relapse of at least 30 days before the baseline visit.
- ✓ Treatment with intravenous corticosteroids completed at least 30 days before the baseline visit (assumption of oral cortisone allowed as long as within 4 mg per day for no longer than 3 days).

Exclusion Criteria

- ✓ Pregnancy or breast-feeding.
- ✓ Depression or other psychiatric disorders.
- ✓ Unwillingness or inability to comply with the requirements of the protocol.
- ✓ Have any contra-indications to treatment with Peg-IFN-beta 1a according to the Summary of Product Characteristics

5. Study population

Full Analysis Set (FAS) consisting of all enrolled patients who took at least one dose of the study medication.

6. Sample size

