In addition, routine clinical assessments will be performed in order to check the safety of the Peg-IFN ongoing treatment.

Laboratory Safety Assessments

At the Investigator's discretion, the following routine laboratory tests can be carried out, in order to monitor the safety profile of the ongoing treatment based on Peg-IFN:

- Hematology: RBC- WBC –Haemoglobin- Haematocrit- MCV- MCH – MCHC - Platelets Count – Lymphocytes- Monocytes – Neutrophils – Eosinophils – Basophils
- Blood chemistry: creatinine, blood urea nitrogen (BUN), alkaline phosphatase, ALT, AST, gamma-glutamyl-transferase (GGT).

A pregnancy hCG test (blood sample) will be performed at the baseline visit (T0) to exclude pregnancy, if applicable (it is not required if the subject is post-menopausal or surgically sterilized).

9. Missing data

For missing data in TSQM-9, MSTCQ and MusiQoI see paragraph Variable of analysis.

For the other variables no imputation technique will be apply.

10. Statistical analysis

The primary and secondary endpoints will be evaluated using a repeated measures ANOVA. The repeated measures ANOVA is used to compare group means on a dependent variable across repeated measurements of time. This statistical method is used for making simultaneous comparisons between two or more means of two or more related, not independent, groups.

However, in addition, it could be useful to apply a general linear mixed model that models for group means as fixed effects while simultaneously modeling for individual subject variables as random effects (12). This kind of model is a subject-specific model and is a choice for analysing longitudinal data. Unlike the repeated measures ANOVA, which requires a complete balanced array of data, the mixed model can accommodate a dataset with a large portion missing. Although the repeated measures ANOVA requires a fixed time schedule among all individual units, the mixed model can accommodate flexible time schedules. Furthermore, rather than treating time as a categorical variable, as in the repeated measures ANOVA, the mixed model is capable of treating time as either a continuous variable or a categorical variable or both.

Spearman's correlation coefficient measures the strength of association between two ranked variables.

Differences will be considered statistically significant if the p-value will be less or equal to a type I error =0.05 (two-sided test).

11. Efficacy data

a. Primary Endpoint Analysis

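### Patients withdrawn for missed doses drop out of the week-12 and week-24 adherence results, because the SAP has no rule for using their early-termination survey

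*Protocol*

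**What the plan says.** **Leaving the study.** Protocol 12.1 lists the reasons for which Peg-IFN must be stopped permanently. One is "At the discretion of the Investigator or Sponsor for noncompliance"; the section does not define noncompliance. It adds: "Subjects discontinuing from study treatment for any of the abovementioned reasons must be permanently withdrawn from the study". Protocol 12.2 separately requires withdrawal when "The subject is unwilling or unable to comply with the protocol".

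**What is collected.** In the Schedule of Events (Protocol 4.2), the row "Assessment of patients' adherence" is marked at T0, T1, T2 and ET. Protocol 12.1 asks investigators to make every effort to hold the ET visit. Drug accountability is marked at T1, T2 and ET, and Protocol 10.2 has sites record dosing compliance and collect used and unused pens.

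**What is analysed.** SAP 5 defines the Full Analysis Set as "all enrolled patients who took at least one dose of the study medication". SAP 9 points to scoring rules for TSQM-9, MSTCQ and MusiQoL, then says: "For the other variables no imputation technique will be apply". Adherence falls in that remainder. SAP 10 names repeated measures ANOVA, "which requires a complete balanced array of data", as the method, and adds that "it could be useful to apply a general linear mixed model". SAP 11.b lists change in the adherence survey at weeks 12 and 24 among the endpoints for the adjusted ANOVA. In SAP 13, tables P21 to P23 summarise dosing over the last 28 days and P40 gives reasons for discontinuation. Tables are repeated by visit where applicable. The ET visit is not mentioned in the SAP text available.

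**The concern.** Being in the Full Analysis Set does not give a patient a value at T1 or T2. A patient removed before T1 has no survey at either visit. One removed between T1 and T2 counts at week 12 but not at week 24. Neither has the complete data that the SAP says the ANOVA needs. The optional mixed model would use the visits that exist, but no rule gives it the ET answers.

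For someone withdrawn because of missed injections, poor adherence is itself the reason for being absent from the adherence result. That is selection on the outcome, and it remains even though the relevant survey is meant to be collected at ET. At stake are the adherent proportion at each visit, the change-from-baseline analysis, and the planned look at how satisfaction relates to adherence, which draws on the same data.

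**Working it through.** **Inputs from the documents.** 275 patients enrolled and drop-out up to 10% (Protocol 16.5, SAP 6). The plan's figure reproduces as 250 × 1.10 = 275. Ten per cent of 275 is 27.5; taking 27 leavers leaves 275 − 27 = 248 at T2.

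**Assumptions (the documents give no adherence rate, noncompliance rate or withdrawal timing).** Completer adherence p is 70% to 95%. Leaver adherence q runs from 50% down to 0. The number of leavers concerned is d. For week 12, 14 of the 27 leave before T1, so 275 − 14 = 261 are observed.

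**Proportion adherent.** With N patients observed, the observed-case proportion is p. With the d leavers included it is (N·p + d·q)/(N + d). The excess is therefore d/(N + d) × (p − q).

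Week 24, N = 248, excess in percentage points:

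| d | d/(N+d) | p=95%, q=0 | p=95%, q=50% | p=70%, q=0 | p=70%, q=50% |
|---|---|---|---|---|---|
| 3 | 3/251 | 1.14 | 0.54 | 0.84 | 0.24 |
| 9 | 9/257 | 3.33 | 1.58 | 2.45 | 0.70 |
| 27 | 27/275 | 9.33 | 4.42 | 6.87 | 1.96 |

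If q = p, the excess is 0 for any d.

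Week 12, N = 261, p = 95%, d = 2: 2/263 × 0.95 = 0.72 points at q = 0, and 2/263 × 0.45 = 0.34 points at q = 50%.

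**Change from baseline.** Let bc and bd be the baseline adherence of completers and leavers. The excess in mean change is d/(N + d) × [(p − bc) − (q − bd)]. With N = 248, d = 9, bc = 80% and p = 95%:
- leavers 80% to 0: 9/257 × (0.15 + 0.80) = +3.33 points
- leavers 80% to 50%: 9/257 × (0.15 + 0.30) = +1.58
- leavers 35% to 50%: 9/257 × (0.15 − 0.15) = 0
- leavers 20% to 50%: 9/257 × (0.15 − 0.30) = −0.53

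The sign depends on the leavers' own baseline, which nobody knows in advance.

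**Survey coverage.** Dosing every two weeks at weeks 0, 2, …, 22 gives 12 injections. The 28 days before week 12 hold those at weeks 8 and 10; the 28 days before week 24 hold those at weeks 20 and 22. That is about 4 of 12. A visit one week early or late still captures two per window. The questionnaire itself is not visible, so the 28-day window is taken from P21. No listed table uses the pen counts or site dosing records that cover the other injections.

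**The case against.** The strongest reply is that the plan already gives some visibility. Because tables are repeated by visit, P21 and P22 could be produced for ET, beside P40's reasons for leaving. That stands as transparency, but it does not bring those patients into the week-12 or week-24 figures.

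Second, the number affected may be very small. Noncompliance withdrawal is discretionary and undefined, it need not mean missed injections, and patients unwilling or unable to comply are excluded at entry. The count could be 0 or 1, and every size above rests on assumed rates. This stands, and it is why the priority is modest.

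Third, an on-treatment reading of adherence is legitimate. Scoring a withdrawn patient as non-adherent at every later visit, after the investigator or sponsor stopped the drug, would measure persistence. This also stands. Such scoring belongs at most in a sensitivity analysis at the next scheduled visit.

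Fourth, ET handling is unspecified for the other endpoints too. That is true, but only for adherence can the outcome itself be the ground for removal.

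**Conclusion.** The gap is real. Followed as written, the plan gives an observed-case adherence result from which patients can be missing because they did not adhere. The adherent proportion is overstated if leavers were less adherent than completers and is unaffected if they were equal. Under the stated assumptions the week-24 excess is about 0.2 to 1.1 points for 3 such leavers and 0.7 to 3.3 for 9; at week 12 it is 0.3 to 0.7 points for 2.

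Three stronger readings are not supported:
- A reader might infer that the change-from-baseline endpoint is inflated. It may be, but the scenarios run from +3.3 through 0 to −0.5, so no direction is established.
- A reader might take 9.3 points as the likely error. It requires all 27 drop-outs, including those leaving for pregnancy or medical reasons, to be wholly non-adherent.
- A reader might conclude that the discontinuation rule is at fault. The fault lies in the analysis rules; withdrawing noncompliant patients can stay.

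This point concerns a secondary endpoint only. Low-to-moderate priority.

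**What to change.** 1. In SAP 11.b and P21, assign the ET adherence survey to the next scheduled visit, for doses due before the stop only. Show how many leavers have no ET survey, and report the survey-only observed-case result beside it. Add a sensitivity line that counts patients withdrawn for dosing noncompliance as not adherent at the next scheduled visit. Patients who leave before T1 then enter at week 12 and not at week 24, so each visit's denominator should be stated.
2. Add one supportive table from pen accountability and site dosing records at T1, T2 and ET: injections taken divided by injections planned while on treatment, for every dosed patient. This covers the injections outside the two 28-day windows.

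Persistence stays in P40, and the discontinuation rule is unchanged. No new visit or procedure is needed. The costs are SAP wording, one added table, classifying each noncompliance withdrawal as dosing or other, some data entry if pen or dosing records are held only at site, and a possibly less favourable adherence figure.

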### **12.2 Withdrawal of Subjects From Study**

Subjects must be withdrawn from the study for any one of the following reasons:

- The subject withdraws consent.
- The subject is unwilling or unable to comply with the protocol.
- The subject meets any of the criteria defined in Section 12.1
- The reason for the subject's withdrawal from the study must be recorded in the subject's CRF.

## 13. EFFICACY ASSESSMENTS

### 13.1. Evaluations concerning the patients' adherence, quality of life, injection-system satisfaction, through the specific tests, including MSTCQ and MusiQoL.

Being this a health outcomes research study, in the present protocol the term *efficacy* refers to the assessment of the following patients' reported parameters, corresponding to the primary and secondary objectives of the study, and to the measurement of the related endpoints:

- overall treatment satisfaction;
- injection system satisfaction;
- adherence to treatment;
- health-related quality of life;
- fatigue.

Demographic (age, gender, education and employment) and medical information (disease duration, previous treatments, comorbidities and concomitant therapies, EDSS score and number of relapses in the previous 12 months) will be obtained at baseline.

All the endpoint-related questionnaires, described below, will be administered at baseline and after 12 and 24 weeks of treatment.

#### a) Patients' Satisfaction assessment

- *Abbreviated Treatment Satisfaction Questionnaire to Medication (TSQM-9)*

The TSQM Version 1.4 is a 14-item psychometrically robust and validated instrument consisting of four scales. The 14 questions were selected from an original set of 55 questions obtained from literature review and focus groups. The four scales of the TSQM include the effectiveness scale (questions 1 to 3), the side effects scale (questions 4 to 8), the convenience scale (questions 9 to 11) and the global satisfaction scale (questions 12 to 14). In the TSQM-9, the five items related to side effects of medication were not included, which creates a need to psychometrically assess the performance of the abbreviated instrument. The TSQM-9 domain scores were calculated as recommended by the instrument authors (10). The TSQM-9 domain scores range from 0 to 100 with higher scores representing higher satisfaction on that domain.

#### b) Patients' adherence assessment

A questionnaire assessing adherence and the reasons for not taking drug at the recommended frequency of administration.

#### c) Patients' Injection-System Satisfaction

- *Adapted Sclerosis Treatment Concerns Questionnaire (MSTCQ)*

The MSTCQ is a validated 20-item patient questionnaire developed to address patient concerns with IFN-beta treatment that are not related to efficacy. It has two domains: injection-system satisfaction and side effects. The side-effects domain comprises 3 subscales: ISRs, global side effects, and FLS.11 All questions in the MSTCQ have a 5-point response choice, with lower total scores indicating better outcomes. A version adapted for Plegridy will be used.

d) Health Related Quality of Life

- *Multiple Sclerosis International Quality of Life questionnaire (MusiQoL)*

MusiQoL version 5.2 (Multiple Sclerosis International Quality of Life) is a multi-dimensional self-administered questionnaire consisting of 31 items describing nine dimensions of health-related quality of life. The nine dimensions assess many aspect of QoL that are specific to MS patients (activities of daily living, psychological wellbeing, symptoms, relationship with friends, relationship with family, sentimental and sexual life, coping rejection, relationship with healthcare system). Items listed in the MusiQoL questionnaire have responses describing frequency/extent of an event on a five-point scale ranging from never/not at all (option 1) to always/very much (option 5). All of the 9 dimensions and the global index are linearly transformed and standardized on a 0-100 scale. Higher scores indicate a better level of health-related QoL for each dimension and for the global index score.

e) Patients' Fatigue

- *Fatigue Severity Scale (FSS)*

This is a specific questionnaire composed of 9 statements on the state of fatigue during the previous week. The answers are within a scale of agreement ranging from 1 to 7, with 1 representing the lowest level of agreement. An overall score of  $\geq 36$  indicates a state of fatigue.

Refer to Section 4.2 for the timing of assessments.

